8.4 Reporting Procedures

8.4.1 Adverse Event Reporting

All adverse events will be collected and reported to the IRB and Namida Lab, Inc. regularly and within 30 days.

8.4.2 Serious Adverse Event Reporting

The study site investigator will complete an SAE Form within the following timelines:

- All deaths and immediately life-threatening events, whether related or unrelated, will be recorded on the SAE Form and submitted to Namida Lab, Inc. within 24 hours of site awareness. See **Section 1, Key Roles** for contact information.
- Other SAEs, regardless of relationship, will be submitted to Namida Lab, Inc. within 72 hours of site awareness.
- All SAEs will be followed until satisfactory resolution or until the site investigator deems the event to be chronic or the adherence to be stable. Other supporting documentation of the event may be requested by Namida Lab, Inc. and should be provided as soon as possible.
- Namida Lab, Inc. will be responsible for notifying the IRB/FDA of any unexpected fatal or life-threatening suspected adverse reaction as soon as possible but in no case later than seven calendar days after Namida Lab, Inc.'s initial receipt of the information.

8.4.3 Unanticipated Problem Reporting

All possible unanticipated problems will be reported to the IRB within five (5) days of receiving notice of the event if the event requires immediate intervention to prevent serious harm to participants or others.

All other possible unanticipated problems will be reported to the IRB as soon as possible. Reported no later than ten (10) business days from the date of the event or from the date the sponsor-investigator is notified of the event.

Incidents or events that meet the OHRP criteria for unanticipated problems require creating and completing an unanticipated problem report form. The site investigator's responsibility is to report unanticipated problems to the study sponsor, Namida Lab, Inc., for further reporting to the IRB.

The unanticipated problem report will include the following information:

- Protocol identifying information: protocol title and number, PI's name, and the IRB project number.

- A detailed description of the event, incident, experience, or outcome.
- An explanation of the basis for determining that the event, incident, experience, or outcome represents an unanticipated problem.
- A description of any changes to the protocol or other corrective actions taken or proposed in response to the unanticipated problem.

Sponsor-investigator must promptly report (according to the above schedule) the following events to the IRB if the events occur within thirty (30) days of participants' active participation:

- Adverse events, which in the opinion of the sponsor-investigator, are both unexpected and related.
- An unanticipated event related to the utility study that exposes individuals other than the participants (e.g., investigators, research assistants, students, the public, etc.) to potential risk.
- Information that indicates a change to the risks or potential benefits of the utility study.

For example:

- An interim analysis or safety monitoring report indicates that the frequency or magnitude of harms or benefits may differ from initially presented to the IRB.
- A paper is published from another study that shows that the study's risks or potential benefits may be different than initially presented to the IRB.
- A breach of confidentiality.
- Incarceration of a participant in a protocol not approved to enroll prisoners.
- Change to the protocol taken without prior IRB review to eliminate an apparent immediate hazard to a participant.
- Complaint of a participant when the compliant indicates unexpected risks or cannot be resolved by the study personnel.
- Protocol violation (meaning an accidental or unintentional change to the IRB-approved protocol) that harmed participants or others or that indicates participants or others may be at increased risk of harm.
- An event that requires prompt reporting to Namida Lab, Inc.
- Namida Lab, Inc. imposed suspension for risk.
- Any other event that indicates participants or others might be at risk of serious, unanticipated harms that are reasonably related to the study.

8.5 Study Halting Rules

Administration and result consultations of the Melody® assay will be halted when three grade 3 AEs are determined to be "probably related." The sponsor investigator will notify the IRB immediately when the third grade 3 event is reported, and enrollment screens will stop accepting new participants.

8.6 Safety Oversight

Safety oversight will be the responsibility of the sponsor principal investigator.

9. Clinical Monitoring

Clinical site monitoring is conducted to ensure that the rights and well-being of human subjects are protected. In addition, the reported study data are accurate, complete, and verifiable, and that the conduct of the study follows the currently approved protocol/amendment(s), with GCP,

and with applicable regulatory requirement(s). The study monitor will perform clinical site monitoring. The appointment and responsibilities of the study monitor are defined in section 13.5.

10. Statistical Considerations

10.1 Statistical and Analytical Plans

An a priori power analysis was conducted using G*Power v3.1.9.2 to determine the minimum sample size required to find significance with a desired level of power set at 0.80 and alpha (a) level at 0.05. Based on this analysis, it was determined that a minimum of 205 participants were required to ensure adequate power for a Pearson's Chi-square Test of Independence. (12, 13, 14) (Appendix L)

Each participant will be required to take an enrollment survey that collects information on race, ethnicity, and socio-economic status. Participant's addresses will be obtained as part of the requisition process for the CLIA lab, from which information on geographic location can be obtained. In addition to the factors listed above, the enrollment survey also collects information on status and type of health insurance, reproductive health, breast health knowledge, prior screening history, and family and personal history of cancer.

The exit survey has been designed to collect information on the participant experience with Melody® and comprehension of the information Melody® relayed through their site clinician. In addition, information is collected on participant's intention to schedule/participate in future screening mammograms and/or change in intention to participate in a previously scheduled screening mammogram.

Data will be analyzed using SPSS Statistics software. To determine the presence of significant changes, Unpaired T-tests or Mann-Whitney U-test will be used with a significance level set at P < 0.05.

Due to the effect of COVID-19 on screening rates, screening mammogram participation rates will be compared to rates reported for the state of Arkansas in 2019.

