10.4 Description of statistical methods

10.4.1 General Approach

For all variables of interest, percent change will be evaluated for statistical significance by Unpaired T-test or Mann-Whitney U-test as appropriate. Statistical significance will be set at $P < 0.05$.

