10.4.5 Adherence and retention analysis

During the participant's journey through the study, there are various points where adherence and retention can be assessed. A log will be generated for each site listing each participant who has enrolled, their contact information, and where they are in the study process.

1. Study enrollment - A list can be generated by the site of participants enrolled. In addition, participants can be tracked via Namida Lab, Inc.'s LIMS system, as an open order will be generated once the participant's enrollment is complete.
2. Sample collection - Once the participant has completed sample collection at their site, the order will be completed, and the sample received by the lab.
3. Exit survey - A notification method will be arranged by site, which will allow site personnel to alert Namida Lab, Inc. when the results have been reported to study participants. Once this has occurred, the participant will be sent an exit survey.
4. After completing the exit survey, the study participant will receive the \$25.00 Walmart

gift card incentive. This will allow the study sponsor to track adherence and retention.

11. Source Documents and Access to Source Data/Documents

A Case Report Form will be completed for each participant enrolled in the clinical study. The investigator-sponsor will review, approve, and sign/date each completed CRF; the investigator-sponsor's signature serves as an attestation of the investigator-sponsor's responsibility for ensuring that all clinical and laboratory data are entered into the CRF are complete, accurate, and authentic. Any missing or spurious data will be accompanied by a note to file in the participant's record, which will clarify its reason and any action taken afterward.

Source Data are the clinical findings and observations, laboratory and test data, and other information in Source Documents. Source Documents are the original records (and certified copies of original records); including, but not limited to, all consent forms, app screens, app-based screening forms, regulatory documents, hospital medical records, physician or office charts, physician or nursing notes, participant diaries or evaluation checklists, pharmacy dispensing records, recorded data from automated instruments, x-rays, etc. When applicable, information recorded on the CRF shall match the Source Data recorded on the Source Documents.

12. Quality Assurance and Quality Control

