 Contraceptive Patch
 Intrauterine device (IUD)
 Vaginal Ring
 None
2. Are you currently using any hormone replacement therapy? (select one)
 Yes No
3. Please select what hormones you are currently taking: (select all that apply)
 Testosterone
 Estrogen
 Progesterone
 Other: _____
4. Hormone replacement medication name if known: _____
5. At what age did your periods begin? _____ (number)
6. Do you still have regular periods? (select one)
 Yes No
7. If you Do Not have regular periods, please select one of the following reasons: (select one)
 Menopause
 Hysterectomy
 Response to Birth Control
 Uterine Ablation
 Other (please describe): _____
 Unknown
8. Do you still have ovaries? (select one)
 Yes No

Section 3: Breast health:

1. Have you ever been told you have dense breast tissue? (select one)
 Yes No
2. Are you currently on, or have you been told, you should be on a high-risk breast cancer screening protocol? (select one)
 Yes No

3. Do you get an annual mammogram for breast cancer screening? (select one)
 Yes No
4. Do you get a bi-annual, every two years, mammogram for breast cancer screening? (select one)
 Yes No
5. When was your last screening mammogram? (enter date or select one)
(mm/dd/yyyy) ____/____/____ Unknown N/A
6. Have you ever received an abnormal screening mammogram? (select one)
 Yes No
7. From your last mammogram, what BI-RADS assessment category was on your mammogram results report? (select one)
 0 - Incomplete - Additional imaging evaluation and comparison to prior mammograms are needed.
 1 - Negative
 2 - Benign (non-cancerous findings)
 3 - Probably benign finding (follow-up in a short time frame is suggested)
 4 - Suspicious abnormality (biopsy should be considered)
 4A - Finding with a low likelihood of being cancer (more than 2% but no more than 10%)
 4B - Finding with a moderate likelihood of being cancer (more than 10% but no more than 50%)
 4C - Finding with a high likelihood of being cancer (more than 50% but less than 95%), but not as high as Category 5
 5 - Highly suggestive of malignancy (appropriate action should be taken)
 6 - Known biopsy-proven malignancy (appropriate action should be taken)
 Unknown

Section 4: Personal history and family history of cancer:

1. Please list below any cancers you have or have had in your lifetime.

No personal history of cancer Personal history unknown

Cancer Type	Year of diagnosis	Treatment	Treatment ongoing

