Provider: [name], MD
Collecting Location: Namida Lab
Sample ID: MEL21000026
Entered by: [name]

Melody Test

Approved By: [name]

Melody Score **-0.509**

Reference Range:

Melody Score Interpretation **Low**

04/16/21 10:41 AM Melody® is an adjunct clinical test that is intended to be based on the independent medical judgment of the ordering physician in conjunction with the patient's complete medical history and the result of standard care testing. It is recommended that a Melody score above 0.1 be clinically correlated with a structural examination of the breast tissue such as mammography.

Melody is not a replacement for a screening mammogram.

Melody Test type: Composite algorithmic analysis of tear protein biomarkers. Quantitative values of individual biomarkers are not reportable and are not associated with individual biomarker result reference ranges.

Precautions and Limitations:
Melody is intended for women ages 40-87 at average risk of developing breast cancer.

Melody may produce a false positive or false negative result. A Melody score below 0.1 does not guarantee the absence of breast cancer. Patients with a Melody score below 0.1 should be advised to continue participating in breast health standard care testing for their age group. A Melody score above 0.1 does not guarantee the presence of breast cancer. Patients with a Melody score above 0.1 should be referred for imaging.

Melody was developed and its performance characteristics determined by Namida Lab, Inc. It has not been cleared or approved by the U.S. Food and Drug Administration. The FDA has determined that such clearance is not necessary. This test is used for clinical purposes. Namida Lab, Inc. is regulated under the Clinical Laboratory Improvement Amendments of 1988 (CLIA) as qualified to perform high-complexity clinical testing.

J. Study Participant Exit Survey/Questionnaire

**VIOLA Study:
Validating Individualized breast cancer screening
by Offering a new Link in Access**

Study Participant Exit Survey

Thank you for taking the time to participate in our study. Please answer the following questions to the best of your knowledge.

Last Name: _____ First Name: _____ Middle Initial: _____

Date of Birth (mm/dd/yyyy) ____/____/____

1. Before enrolling in the VIOLA Study, did you have an appointment for a screening mammogram?
 Yes No

2. How comfortable were you with the sample collection process? (circle one)

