Very Uncomfortable	Uncomfortable	Comfortable	Very Comfortable
1	2	3	4

3. How would you rate the likelihood that you could do the sample collection process on your own? (circle one)

Very Unlikely	Unlikely	Likely	Very Likely
1	2	3	4

4. How would you rate your ability to understand your Melody® results? (circle one)

Very Difficult	Somewhat Difficult	Somewhat Easy	Very Easy
1	2	3	4

5. How would you rate the explanation of your Melody® results by your provider? (circle one)

Unacceptable	Poor	Fair	Excellent
1	2	3	4

6. How would you rate the ability of your provider to answer your questions about Melody®? (circle one)

Unacceptable	Poor	Fair	Excellent
1	2	3	4

7. How would you rate the length of time it took to get your results back from the Melody® test? (circle one)

Unacceptable	Poor	Fair	Excellent
1	2	3	4

8. How would you rate the reliability of the Melody® test? (circle one)

Unacceptable	Poor	Fair	Excellent
1	2	3	4

9. How would you rate your willingness to use Melody® to help you make decisions about your breast health in the future? (circle one)

Very Unlikely	Unlikely	Likely	Very Likely
1	2	3	4

10. After receiving your Melody® results, are you going to schedule/complete a screening mammogram and why?

Yes No

Explanation: _____

11. May we contact you after you participate in the VIOLA Study if you are planning to have a screening mammogram?

Yes No

If yes, please provide the best method of contact (mailing address/phone number /email):

K. Study Site Provider Exit Survey/Questionnaire

**VIOLA Study:
Validating Individualized breast cancer screening
by Offering a new Link in Access**

Study Provider Exit Survey

Site Location ID: _____ Site Location PI: _____

1. How would you rate the process of the sample collection? (circle one)

Very Difficult	Somewhat Difficult	Somewhat Easy	Very Easy
1	2	3	4

2. How would you rate how the understandability of the Instructions for use for collecting tear samples? (circle one)

Very Difficult	Somewhat Difficult	Somewhat Easy	Very Easy
1	2	3	4

3. How would you rate the integration of sample collection in your clinic workflow? (circle one)

Very Difficult	Somewhat Difficult	Somewhat Easy	Very Easy
1	2	3	4

4. How likely do you think an individual could do this collection process at home? (circle one)

Very Unlikely	Unlikely	Likely	Very Likely
1	2	3	4

5. How would you rate the length of time to get results back on Melody®? (circle one)

Unacceptable	Poor	Fair	Excellent
1	2	3	4

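### Intention to have a mammogram is asked only after the Melody result, so for women without an appointment no change in intention can be measured

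*Protocol*

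**What the plan says.** Section 10.1 describes two things that the exit survey gathers about intention. The first is general: "information is collected on participant's intention to schedule/participate in future screening mammograms". The second is introduced by and/or and is narrower: "change in intention to participate in a previously scheduled screening mammogram". Section 10.4.1 adds that, for all variables of interest, "percent change will be evaluated for statistical significance", and names only unpaired tests.

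The forms themselves are in the appendices:

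- **Exit survey, Appendix J, item 10:** "After receiving your Melody® results, are you going to schedule/complete a screening mammogram and why". It takes Yes or No plus an explanation.
- **Exit survey, Appendix J, item 1:** "Before enrolling in the VIOLA Study, did you have an appointment for a screening mammogram". It takes Yes or No.
- **Enrollment survey, Appendix D, Section 3:** "Do you get an annual mammogram for breast cancer screening", a matching item on two-yearly mammograms, and the date of the last one. None of these asks what the woman intends to do next.

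Section 10.4.5 sets the timing. The site tells the sponsor when results have been given to the participant, and then: "Once this has occurred, the participant will be sent an exit survey".

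**The concern.** Section 4.1 asks how using Melody before mammography affects participation in screening. Exit item 10 is the only forward-looking answer on mammography that the schedule obtains from each woman. Under 7.1.4 her participation ends with the exit survey, and the schedule of events in 7.3.6 has no row for completing a mammogram. Item 11 only asks permission for later contact, and item 15 of the provider survey in Appendix K is a count per provider.

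A Yes to item 10 is therefore likely to be read as a sign that Melody moved the woman. But she may have intended a mammogram all along, and the forms do not tell these cases apart. A statistical analysis plan written later cannot repair this, because an answer not taken before the result cannot be recovered afterwards.

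**Working it through.** **The plan's own figure.** The only design calculation is the sample size in Appendix L: proportions 0.50 and 0.70, two-sided alpha 0.05, power 0.80, equal groups.

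n per group = [1.960 × √(2 × 0.60 × 0.40) + 0.842 × √(0.50 × 0.50 + 0.70 × 0.30)]² / 0.20² = [1.358 + 0.571]² / 0.04 = 93.

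That gives 186 in total, and 186 × 1.1 = 204.6, rounded up to 205, as stated. It concerns compliance in two groups, and the present point does not depend on it.

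**What is recorded, and when**

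| Woman | Before Melody | After result | What the pair can show |
|---|---|---|---|
| Had an appointment | Appointment, recalled at exit (item 1) | Item 10 | Kept or dropped |
| Had no appointment | No intention recorded; only habit and last mammogram date | Item 10 | Nothing about change |

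**Women with an appointment.** If the appointment stands in for intention, the starting value is Yes for all of them. With a proportion q answering Yes at exit, the net change is q − 1, which is zero or negative. A gain cannot appear.

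**Women without an appointment.** Let q be the proportion answering Yes at exit and b the unrecorded proportion who intended a mammogram beforehand. Net change = q − b, with b anywhere from 0 to 1. The limits are therefore q and q − 1.

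In terms of movement, take q = 0.75 (assumed). Between 0 and 75 points could have moved from No to Yes, and between 0 and 25 points from Yes to No. The net runs from +75 to −25.

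Net change in percentage points, for assumed values of q (the documents give none):

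| Yes at exit | b = 0% | b = 50% | b = 100% |
|---|---|---|---|
| 60% | +60 | +10 | −40 |
| 70% | +70 | +20 | −30 |
| 75% | +75 | +25 | −25 |
| 80% | +80 | +30 | −20 |

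Each row spans q − (q − 1) = 100 points. The exit answer shifts the range but does not narrow it, whatever the sample size. Habit and last mammogram date make some values of b more plausible than others, but they record past behaviour and do not fix b.

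**The case against.** The strongest reply is that 10.1 does not promise what is missing. Its clause on change is limited to a mammogram already scheduled, and there items 1 and 10 together supply a crude answer. This stands. A reader might infer that 10.1 claims to measure change in every woman and then fails to; the wording does not support that. For women without an appointment this is a gap in the design, not a contradiction in the text.

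Second, intention is not an endpoint under test. The hypotheses in 10.2 and the table shells in 10.4.2 and 10.4.3 concern participation against 2019. A reader might take the percent-change sentence in 10.4.1 as scheduling a test of change in intention, but nothing in the protocol names intention there. This also stands and limits the weight of the point.

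Third, it would be too strong to say that item 10 is the exit survey's only answer on mammography, or that an intention pair is the only possible within-woman contrast. Items 1 and 11 also concern mammography, and the enrollment history gives a behavioural baseline.

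Fourth, a baseline question would not show that Melody caused a change. Under 4.1 every participant receives the test, and the results script in 7.3.3 includes a recommendation for a screening mammogram. This is correct, and the reporting must say so.

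None of these replies supplies a prior intention for women without an appointment.

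**Conclusion.** The point holds as a cheap improvement to supportive survey data. As the forms stand, item 10 can be described but cannot show change in women without an appointment. The range of possible net change is 100 points wide at any exit proportion, for example +75 to −25 at an assumed 75% Yes. Among women with an appointment, only a loss of intention can be registered, and that rests on treating a recalled appointment as intention.

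This conclusion rests on the survey forms as printed in Appendices D and J and on the timing in 10.4.5. The percentages are illustrations; the lack of a prior value does not depend on them. The tests of participation in 10.2 are not affected.

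**What to change.** 1. Add one item to Appendix D, Section 3, with the wording of exit item 10 but without its opening clause about having received Melody results. It should be answered before tear collection; 7.1.4 already places the enrollment questionnaires ahead of the sampling visit.
2. Analyse the completed pairs with McNemar's test and give the paired difference with its confidence interval, overall and by High or Low classification. The unpaired tests named in 10.4.1 do not suit two answers from the same woman.
3. Report the result as before/after change. State that, without a control group, it cannot separate Melody from the consultation, the clinician's recommendation or the effect of being asked.
4. If the item is not added, state in 10.1 that exit item 10 is descriptive only.

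The cost is one extra question and an IRB-approved form change. Asking about intention at enrollment may itself prompt some women, probably slightly; the documents give no figure for this. The change needs to be made before women receive results.
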